3.2.2 Dose Expansion

For the SL-172154 + PLD expansion cohort, the goal is to enroll approximately 20 subjects treated at the potential RP2D in either dose expansion or dose escalation. The sample size of 20 is primarily chosen to obtain a preliminary assessment of the antitumor activity with a certain degree of precision. Table 4 provides the 90% confidence interval (CI) based on exact probability method for a range of possible responses out of 20 subjects. Approximately 14 of these subjects at the potential RP2D will be enrolled in the dose expansion cohort.

Table 4 Response Rate 90% CI out of 20 Subjects

#Responses/20 Subjects	Response Rate	90% CI
2	10%	1.8%, 28.3%
4	20%	7.1%, 40.1%
6	30%	14.0%, 50.8%
8	40%	21.7%, 60.6%
10	50%	30.2%, 69.8%
12	60%	39.4%, 78.3%
14	70%	49.2%, 86.0%
16	80%	59.9%, 92.9%
18	90%	71.7%, 98.2%

For the SL-172154 + MIRV expansion cohort, the goal is to enroll approximately 20 subjects treated at the potential RP2D for each of the following three tumor FR α expression subgroups in either dose expansion or dose escalation: high (PS2+ \geq 75%), medium (PS2+ \geq 50% and $<$ 75%), and low (PS2+ \geq 25% and $<$ 50%). The sample size of 20 is primarily chosen to obtain a preliminary assessment of the antitumor activity with a certain degree of precision.

Approximately 64 subjects treated at the potential RP2D will be enrolled in the dose expansion cohort.

Each expansion cohort will allow further characterization of the safety profile of SL-172154 in combination with either PLD or MIRV, with particular emphasis on toxicities leading to discontinuation of SL-172154 and the combination agents. Continuous toxicity monitoring based on a Pocock-type stopping boundary [Ivanova, 2005] will be used within each expansion cohort. Accrual will be temporarily stopped if an excessive number of subjects discontinue SL-172154 and a combination agent due to toxicities.

In the JAVELIN Ovarian 200 study, the discontinuation rate in the PLD monotherapy group due to AEs was 11% and treatment related AEs leading to treatment discontinuation was 7% [Pujade-Lauraine, 2021], thus a 20% rate of AE leading to treatment discontinuation regardless of causality is selected for the SL-172154 + PLD expansion cohort. Enrollment to the SL-172154 + PLD expansion cohort will be temporarily stopped if an excessive number of subjects experience AEs leading to treatment discontinuation; that is, if the number of subjects with AEs leading to treatment discontinuation is equal to or more than b_n out of n subjects as described in the table below. The sequential stopping boundaries are selected to have at least 70% probability to temporarily stop when the underlying true rate of subjects with AEs leading to treatment discontinuation is $>30\%$.

Number of subjects, n	1	2	3	4	5	6	7	8	9	10	11	12	13	14	15	16	17	18	19	20
Boundary, b_n	-	2	3	3	3	3	4	4	4	4	4	4	5	5	5	5	5	6	6	6

In the IMGN853-0401 study, 15% of the subjects at 6 mg/kg MIRV monotherapy discontinued treatment due to AEs (MIRV IB), thus a 20% rate of AE leading to treatment discontinuation regardless of causality is selected for the SL-172154 + MIRV expansion cohort. Enrollment to the SL-172154 + MIRV expansion cohort will be temporarily stopped if an excessive number of subjects experience AEs leading to treatment discontinuation; that is, if the number of subjects with AEs leading to treatment discontinuation is equal to or more than b_n out of n subjects as described in the table below. The sequential stopping boundaries are selected to have at least

82% probability to stop when the true underlying rate of subjects with AEs leading to treatment discontinuation is >30%.

Number of subjects, n	1	2	3	4	5	6	7	8	9	10	11	12	13	14	15	16	17
Boundary, b_n	-	-	3	4	4	4	5	5	5	5	6	6	6	6	7	7	7
Number of subjects, n	18	19	20	21	22	23	24	25	26	27	28	29	30	31	32	33	34
Boundary, b_n	7	8	8	8	8	9	9	9	9	10	10	10	10	11	11	11	11
Number of subjects, n	35	36	37	38	39	40	41	42	43	44	45	46	47	48	49	50	51
Boundary, b_n	11	12	12	12	12	12	13	13	13	13	14	14	14	14	15	15	15
Number of subjects, n	52	53	54	55	56	57	58	59	60	61	62	63	64	65			
Boundary, b_n	15	15	15	16	16	16	16	16	17	17	17	17	17	18			

3.3 Sample Size

The planned sample size is approximately 102 subjects, depending on the number of dose levels evaluated in dose escalation for each of the combinations. Approximately 24 subjects will be enrolled in dose escalation cohorts (12 subjects in PLD cohorts and 12 subjects in MIRV cohorts) and approximately 78 subjects will be enrolled in a dose expansion cohort (an additional 14 subjects at the selected dose in PLD cohort and an additional 64 subjects at the selected dose in MIRV cohort).

All subjects with tumors that are FR α positive (PS2+ $\geq 25\%$) enrolled in the MIRV combination cohort will be retrospectively binned in expression subgroups (high, medium, low) for study analysis. The goal is to enroll approximately 20 subjects at the potential RP2D in either dose expansion or dose escalation for each of the following three tumor FR α expression subgroups: high (PS2+ $\geq 75\%$), medium (PS2+ $\geq 50\%$ and $< 75\%$), and low (PS2+ $\geq 25\%$ and $< 50\%$). This estimation is based on the anticipated frequency of subjects with high grade serous ovarian cancer who fall into each of these FR α expression subgroups. If this distribution is not achieved in any subgroup, approximately 10 additional subjects may be enrolled in this expansion cohort in order to achieve it.

NOTE: The planned sample sizes may be revised if additional dose levels are evaluated or if more subjects (i.e., subjects available for dosing beyond the number required in a cohort) are enrolled than anticipated. The actual number of subjects to be enrolled for each combination dose escalation will depend upon the number of dose levels evaluated and the number of DLTs observed for each dose level and related dose escalation/stay/de-escalation decision. The Sponsor, in consultation with the Safety Monitoring Committee (SMC), may also elect to add subjects to the dose escalation cohorts if additional data is needed to select the dose level for the dose expansion cohort.

3.4 Study Treatment Discontinuation Criteria

A subject will receive the assigned study treatment (e.g., SL-172154 and PLD or SL-172154 and MIRV) until any of the following events occur during the study:

- Documented disease progression (radiological or clinical)
- A subject suffers an AE that, in the judgement of the investigator, Sponsor, or medical monitor, presents an unacceptable risk to the subject
- General or specific changes in the subject's condition (e.g., a significant intercurrent illness or complication) that, in the judgement of the investigator, are unacceptable for further administration of study treatment
- Subject decides to discontinue further study treatment
- Occurrence of pregnancy
- Significant non-compliance with protocol requirements
- Death
- Termination of the study by Sponsor

If one agent in the assigned regimen is permanently discontinued for any reason, at the investigator's discretion, the subject may continue to receive the other agent in the assigned regimen as monotherapy until meeting one of study treatment discontinuation criteria.

In the event of permanent discontinuation of all study treatment, subjects should be strongly encouraged to complete all scheduled assessments at the Post Treatment visit and the Survival Follow-up contacts.

3.5 Duration of Follow-up

Subjects who are withdrawn from study treatment for unacceptable AE(s) should be followed until the event(s) are resolved, the subject is lost to follow-up, the AE is otherwise explained, or further recovery is not deemed to be feasible. Data on these events should be collected on the AE eCRF.

Subjects who permanently discontinue study treatment for reasons other than progression will continue with disease assessments until progression or start of another anti-cancer therapy.

Subjects who discontinue study treatment for any reason other than withdrawal of consent will be followed for survival and will be contacted approximately every 3 months until death or the end of the study, whichever occurs first. During Survival Follow-up, the start date of the first anticancer therapy will be collected and entered in the Electronic Data Capture (EDC).

3.6 End of Study

The end of study is defined as the point of final data capture (e.g., the point at which all required data has been collected to answer the research questions in the protocol) or date the study is closed by the Sponsor, whichever occurs first.

After the end of study, subjects who are still in survival follow-up part of the study should receive standard of care treatment as determined by their health care provider after completion of the study.

3.7 Study Assessments and Procedures

The detailed study assessments and procedures are described in Section 6 of the protocol.

4. ANALYSIS POPULATIONS

The populations defined for analysis will include the following:

Population	Description
Screened	All subjects who have signed the main study Informed consent form (ICF).
Screen Failures	All subjects who have signed the main study ICF but have not received any study treatment.
All Treated	All subjects who receive at least one dose of study drug (SL-172154, PLD, or MIRV). Safety data will be evaluated based on this population.
DLT Evaluatable	All subjects enrolled in the dose escalation cohorts who receive at least 50% of the scheduled doses of SL-172154 and 1 dose of PLD or MIRV and complete the safety follow-up through the DLT evaluation period or experience any DLT during the DLT evaluation period. DLT evaluable subjects will be used to guide dose escalation and to determine the MTD or MAD.
Response Evaluatable	Subjects in the All Treated Population who have either had at least one post-baseline disease assessment or who have discontinued study treatment due to disease progression or death before any post-baseline disease assessment.
SL-172154 Pharmacokinetic	Subjects in All Treated Population who have at least one post SL-172154 dose PK sample obtained and analyzed.
SL-172154 Immunogenicity	Subjects in the All Treated Population who have at least one post SL-172154 dose immunogenicity measurement.
MIRV Pharmacokinetic	Subjects in All Treated Population who have at least one post MIRV dose PK sample obtained and analyzed.
MIRV Immunogenicity	Subjects in the All Treated Population who have at least one post MIRV dose immunogenicity measurement.
MIRV FRa Pre-screened	All subjects in MIRV regimen who have signed the pre-screen informed consent form for FRa test.

5. GENERAL ANALYSIS CONSIDERATIONS

5.1 Data Analysis During Dose Escalation

During the dose escalation, the number of subjects with DLTs will be determined after each cohort of approximately 3 subjects has been evaluated for DLT. The summary of DLTs will be based on the DLT Evaluatable Population; the number of subjects with DLTs will be summarized

by dose level for each of the combination dose escalation cohorts. Select AE summary tables and listings may be provided during dose escalation to support dose escalation decisions.

5.2 Reporting Conventions

The statistical analyses will be reported using summary tables, figures, and data listings. The International Conference on Harmonisation (ICH) numbering convention will be used for tables, listings, and figures.

Data from all participating sites will be pooled prior to data summary or analysis. It is anticipated that subject accrual will be spread thinly across sites and summaries of data by site would be unlikely to be informative and will not, therefore, be provided.

Separate summary tables will be provided for each combination regimen (SL-172154 + PLD and SL-172154 + MIRV). Unless specified otherwise, the tables will be presented for each dose level of SL-172154 in dose escalation and dose expansion, subjects receiving the same dose level of SL-172154 from dose escalation and expansion cohorts combined, and all subjects receiving the same combination regimen. The study-level summary for the two regimens combined will be provided for demographic and baseline characteristics and other data if deemed necessary. Select safety summary tables may be provided for the dose escalation cohorts.

Separate listings will be provided for each regimen (SL-172154 + PLD and SL-172154 + MIRV). The study drug exposure listings will be presented by cohort (dose escalation/dose expansion), dose level and date of first dosing. All other individual listings will be presented by cohort (dose escalation/dose expansion), dose level and subject, unless specified otherwise. Data from all assessments, whether scheduled or unscheduled, will be included in the listings. Listings will present the data in their original format (without any imputation), unless specified otherwise.

Summaries by planned time point will include data from scheduled assessments and all data will be reported according to the nominal visit for which it will be recorded (i.e., no visit windows will be applied). Unscheduled data, when summarized, will be included only in calculation of the maximum or minimum value over time such as worst-case post-baseline. If multiple assessments are reported on the same date for the same scheduled planned time, then the worst-case result will be analyzed.

Continuous variables will be summarized with means, standard deviations, medians, minimums, and maximums. The precision of the original measurements will be maintained in summaries and listings, when possible. Generally, means and medians will be presented to one more decimal place than the raw data, and the standard deviations will be presented to two more decimal places than the raw data.

Categorical variables will be summarized by counts and by percentages of subjects in the corresponding categories. Percentages are routinely based on the total number of the specified population N if not specified otherwise. For frequency counts, categories whose counts are zero will be displayed for the sake of completeness. For example, if none of the subjects discontinue

due to “lost to follow-up”, this reason will be included in the table with a count of 0. Categories with zero counts will not have zero percentages displayed.

All confidence intervals (CIs) will be constructed at the 95% confidence level, unless specified otherwise.

All analyses and tabulations will be performed using SAS® v9.4 or above.

5.3 Data Handling

The following sections provide a general description of the derived and transformed variables used to describe and analyze the data.

5.3.1 Premature Withdrawal and Missing Data

Subjects who prematurely withdraw from the study will be included in analyses up to the time of withdrawal, regardless of the duration of treatment and survival follow-up.

Missing data occurs when any requested data is not provided, leading to blank field on the collection instrument. Answers such as “Not applicable”, “Not evaluable”, etc. are not considered to be missing data and should be displayed as such.

For the time to event endpoints including DOR, PFS and OS, the missing data handling method will be censoring. Censoring mechanisms for these endpoints are described in Section 7.

All time to event endpoints will be analyzed using suitable statistical methods.

In the event that the study is prematurely discontinued, a review will be carried out by the study team to assess which statistical analyses are still considered appropriate.

5.3.2 Baseline and Change from Baseline

Unless otherwise specified, the baseline value is defined as the last value obtained on or before the date and time of the first dose of any study drug (SL-172154, PLD or MIRV). Post-baseline values are defined as value obtained after the first dose of study drug.

Change from baseline is calculated as:

- Post-baseline value - baseline value

Percent change from baseline is calculated as:

- $(\text{Post-baseline value} - \text{baseline value}) * 100 / \text{baseline value}$

If either baseline or post-baseline value is missing, the change from baseline and percent change from baseline will be missing.

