6.1 Schedule of Assessments: SL-172154 + PLD Cohorts (Dose Escalation and Dose Expansion)

Cycle Length = 28 days	Assessment ^b	CYCLE 1 (C1)				CYCLE 2 (C2)			CYCLE 3 (C3) and Subsequent Cycles			PTV ^q	SFU ^r	
		Screening ^a	D1	D8	D9	D15	D1	D8	D15	D1	D8	D15		
Informed consent	X													
Eligibility criteria	X ^c	X												
Demographics	X													
Medical and disease history	X													
Cancer treatment history	X													
Type and screen (ABO/Rh), Blood phenotyping, DAT ^d	X													
TSH, free T4 ^e	X													
Antiviral testing (HBV/HCV) ^f	X													
Record historical BRCA, HRD status (if known)	X													
12-lead ECG ^g	X													
ECHO/MUGA ^h	X												X ⁱ	X
Physical examination ^j	X	X	X			X	X		X	X				X
Vital signs ^h	X	X	X			X	X	X	X	X	X	X		
Pulse oximetry ^h	X	X	X			X	X	X	X	X	X	X		
Height (screening only) / weight	X	X					X			X				
ECOG performance status	X	X	X			X	X		X	X				X
Pregnancy test ^k (serum or urine, FCBP only)	X												X ⁱ	X ⁱ
Clinical chemistry ^l	X	X	X	X		X	X	X	X	X				X
Hematology ^l	X	X	X	X		X	X	X	X	X				X
Coagulation ^l (PT, aPTT, INR, d-dimer, fibrinogen)	X				X									
Ferritin	X				X									
C-reactive protein	X													
Haptoglobin	X				X									

Assessment ^b	Screening ^a	CYCLE 1 (C1)			CYCLE 2 (C2)			CYCLE 3 (C3) and Subsequent Cycles			PTV ^q	SFU ^r	
		D1	D8	D9	D15	D1	D8	D15	D1	D8	D15		
Blood sample for SL-172154 PK ^k			X	X	X		X						
Blood sample for SL-172154 ADA ^k			X		X		X			X ^{k1}		X ^{k2}	
Blood sample for cytokines ^l			X	X	X								
Blood sample for receptor occupancy ^l			X	X	X								
Scans for disease assessment ^m	X								X ^m			X ^m	
CA-125 ^m	X								X ^m			X ^m	
SL-172154 administration ⁿ			X		X		X	X		X	X		
PLD administration ^o		X				X			X				
Concomitant medications	X	←----- Continuous Monitoring During Treatment Phase of the Study -----→										X	
Adverse events ^p	X	←----- Continuous Monitoring During Treatment Phase of the Study -----→										X	
Survival contact ^r (q3 months ± 14d)													X

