- o. **PLD Administration:** PLD will be administered according to the dosing schedule provided. If the start of a subsequent cycle (e.g., Day 1) is delayed, the current cycle length is extended (e.g., the cycle lasts longer than 28 days). In addition, length of subsequent cycles will remain unchanged (i.e., 28 days for PLD Cohort).
- p. **AE Monitoring:** Subjects will be followed continuously for AEs during the study and for 30 days after the last dose of SL-172154. After a subject is discontinued from SL-172154 due to progressive disease or for other reasons, any ongoing AE should be followed until resolution (or return to baseline) and documented in the eCRF. If another anti-cancer agent is started within 30 days after the last dose of SL-172154, only SAEs and AEs that occur prior to the start of the new anticancer therapy should be recorded. In the event of a continuing SAE, the subject should be asked to return for follow-up until the SAE has resolved or is deemed to be continuing indefinitely. AEs will be characterized per NCI-CTCAE criteria v5.0 and events recorded in the eCRF
- q. **Post-Treatment Visit (PTV):** visit should occur 30 days (± 7 days) after the last dose of study treatment. If the subject is going to start a new anticancer therapy before the PTV due date, PTV should be conducted prior to starting the new therapy.
- r. **Survival Follow-Up (SFU):** All subjects will be contacted after discontinuing study treatment to collect survival status. Subjects should be contacted every 3 months (± 14 days) from the PTV until death, withdrawal of consent, lost to follow-up or end of study. Contact may include clinic visit, telephone contact, email or mail, chart review, or obituary notice to document survival status. Initiation of any subsequent anti-cancer therapy should also be reported.

6.1.1 PK, ADA, Cytokines and Receptor Occupancy (SL-172154 + PLD Dose Escalation and Dose Expansion Cohorts)

CYCLE 1	C1D1		C1D8							C1D9	C1D15						
	Predose ¹	2h post EOI	Predose ¹	EOI	0.5h post EOI	1h post EOI	1.5h post EOI	2h post EOI	4h post EOI		Predose ¹	EOI	0.5h post EOI	1h post EOI	1.5h post EOI	2h post EOI	4h post EOI
Blood sample for SL-172154 PK ^{2,3,4,5,6}			X	X	X	X	X	X	X	X	X	X	X	X	X	X	X
Blood sample for SL-172154 ADA ⁶			X								X						
Blood sample for cytokines ^{3,5}			X					X		X		X					X
Blood sample for Receptor Occupancy ^{3,5}			X		X					X		X		X			

CYCLE 2	C2D8								

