9.2 Statistical Analysis

Complete details of the statistical analysis will be provided in the Statistical Analysis Plan (SAP). Any deviations from, or additions to, the original analysis plan described in this protocol will be documented in the SAP and final study report.

When determining the RP2D, the totality of the safety, tolerability, PK, PD, and efficacy data collected during both dose escalation and dose expansion is taken into consideration.

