9.2.1 Analysis Populations

The populations defined for analysis will include the following:

Population	Description
Screened	All subjects who have signed the main study ICF
Screen Failures	All subjects who have signed the main study ICF but have not received any study treatment.
All Treated	All subjects who receive at least one dose of SL-172154, PLD, or MIRV. Safety data will be evaluated based on this population.

Population	Description
DLT-Evaluable	All subjects enrolled in the dose escalation cohorts who receive at least 50% of the scheduled doses of SL-172154 and 1 dose of PLD or MIRV and complete the safety follow-up through the DLT evaluation period or experience any DLT during the DLT evaluation period. DLT-evaluable subjects will be used to guide dose escalation and to determine the MTD or MAD.
Response-Evaluable	Subjects in the All Treated Population who have either had at least one post-baseline disease assessment or who have discontinued study treatment due to disease progression or death before any post-baseline disease assessment.
Pharmacokinetic	Subjects in All Treated Population from whom at least one post-baseline PK sample is obtained and analyzed
Pharmacodynamic	Subjects in the All Treated Population for whom a baseline and at least one on-treatment PD sample is obtained and analyzed.

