9.2.7 Pharmacodynamics Analysis

The PD data analysis will be based on the PD population. PD biomarkers values will be summarized descriptively by SL-172154 dose level for each combination regimen.

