To assess the pharmacokinetic profile of SL-172154 when administered with PLD or MIRV in subjects with platinum-resistant ovarian, primary peritoneal, or fallopian tube cancer	
 Maximum observed concentration (C_{max}), time at which the maximum concentration is observed (T_{max}), and minimum observed concentration (C_{min}) following single and multiple doses of SL-172154 Area under the serum concentration-time curve (AUC) Terminal elimination half-life ($t^{1/2}$), Clearance (CL) and Volume of Distribution (V_z), as data permit
To assess the pharmacokinetic profile of MIRV when administered with SL-172154 in subjects with platinum-resistant ovarian, primary peritoneal, or fallopian tube cancer	
 PK exposure evaluation of MIRV, total antibody, and payload (DM4 and S-methyl DM4)
Exploratory Objectives	
To identify and assess pharmacodynamic biomarkers associated with ovarian cancer or the mechanism of action of SL-172154, PLD, or MIRV following treatment with SL-172154 administered with PLD or MIRV in subjects with platinum-resistant ovarian, primary peritoneal, or fallopian tube cancer	
 Changes from baseline in select cytokines Changes in immune cell subsets CD47 and CD40 expression Target-associated regulatory networks Genomic alterations which may correlate with drug safety or efficacy
To explore the association of biological/clinical endpoints with PK parameters of SL-172154 administered with PLD or MIRV in subjects with platinum-	
 To assess the relationship between SL-172154 PK exposure and the anti-tumor activity and safety of SL-172154, if feasible

Objective	Outcome Measure
resistant ovarian, primary peritoneal, or fallopian tube cancer	
Estimate overall survival (OS)	
 • OS: time from first dose to death

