11. CHANGE FROM PROTOCOL-SPECIFIED ANALYSES

There are no changes from the protocol-specified analyses.

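### The SAP leaves out the protocol's pharmacodynamic population and summary while declaring no changes, and its default baseline precedes every blood cytokine sample on the current schedule

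*SAP*

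**What the plan says.** Protocol 9.2.1 defines a Pharmacodynamic population: treated subjects "for whom a baseline and at least one on-treatment PD sample is obtained and analyzed". Protocol 9.2.7 bases the PD analysis on that population and states that "PD biomarkers values will be summarized descriptively by SL-172154 dose level for each combination regimen". Protocol 9.2 adds: "Any deviations from, or additions to, the original analysis plan described in this protocol will be documented in the SAP and final study report".

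SAP Section 11 reads in full: "There are no changes from the protocol-specified analyses". SAP Section 2 keeps the exploratory outcome "Changes from baseline in select cytokines" and keeps PD effects among the measures for selecting the recommended Phase 2 dose.

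SAP 5.3.2 sets baseline, unless another rule is given, as the "last value obtained on or before the date and time of the first dose of any study drug (SL-172154, PLD or MIRV". If the baseline or the post-baseline value is missing, the change is set to missing.

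The schedule rows at issue are "Blood sample for cytokines" (Protocol 6.1, with its counterpart in 6.2) and "Blood sample for Receptor Occupancy" (Protocol 6.1.1, with its counterpart in 6.2.1).

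**The concern.** There are two linked problems.

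First, an analysis that the protocol specifies has dropped out of the SAP, and the section meant to record such departures says there are none. A reader who relies on Section 11 would not learn that cytokine, receptor-occupancy and biopsy data have no planned output.

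Second, the default baseline is tied to the first dose of any agent. SL-172154 starts a week after PLD or MIRV, and blood PD sampling is timed to SL-172154. If PD is restored without attention to this, the one PD outcome that names a change from baseline comes out missing by rule.

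At stake is the final PD analysis and report, not the conduct of the trial.

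**Working it through.** The plan states no figure on this point, so there is none to reproduce. The check sets the documents side by side and adds up planned numbers.

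**1. Protocol against SAP**

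| Item | Protocol | SAP |
|---|---|---|
| PD population | Defined in 9.2.1 | None of the 10 populations in Section 4 |
| PD analysis | 9.2.7 | None; Section 9 is PK, 10 immunogenicity, 11 changes |
| PD outputs | Descriptive summary by dose level and regimen | None in 13.1, 13.2 or 13.3 |
| Departures | To be documented in the SAP (9.2) | None declared (Section 11) |

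The output lists also carry items marked as not needed for the abbreviated report. PD is not among those either, so a shortened report does not explain the gap.

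**2. Dosing against sampling**

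- First study drug: PLD or MIRV on Day 1 of Cycle 1. SL-172154 is given on Days 8 and 15 (Protocol 3.2.1, 3.2.2).
- Blood cytokines and receptor occupancy: C1D8, C1D9 and C1D15 only. The first sample is C1D8 predose. The screening and C1D1 cells are empty in both main schedules (6.1, 6.2), and both detailed schedules (6.1.1, 6.2.1) agree.
- C1D8 predose comes 7 days after the first study drug, so SAP 5.3.2 classes it as post-baseline. No scheduled blood PD sample qualifies as baseline.
- The SAP gives its own reference point for SL-172154 ADA, the first SL-172154 predose sample (10.1). It gives none for cytokines or receptor occupancy.

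**3. Planned subjects with blood PD sampling (current schedule)**

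- PLD: 12 escalation + 14 expansion = 26 (Protocol 9.1.4).
- MIRV escalation: 12 (9.1.4).
- MIRV expansion: about 25 of the 64 (6.2.1).
- Total: 26 + 12 + 25 = about 63.

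With a scheduled baseline under SAP 5.3.2: 0 of about 63. With the last value before the first SL-172154 dose as baseline: up to about 63.

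**4. Which PD measures are affected**

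- Cytokines: directly, because change from baseline is the named outcome.
- Receptor occupancy: same sampling gap, but no change-from-baseline outcome is named. Protocol 6.9 speaks of calculating occupancy and comparing it across dose groups. It is affected only through the default rule and, if that rule is applied, through the PD population's baseline requirement.
- Tumour biopsies: not affected. MIRV expansion has a screening biopsy (Protocol 6.10.1), which is a valid default baseline.
- PD population: if the SAP default is read into Protocol 9.2.1, no PLD subject on the current schedule qualifies, because PLD has no biopsies and no blood PD sample before Day 1 dosing.

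**5. A related label**

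SAP Table 9 ties the first-dose formulas for CL and Vz to C1D1, when no SL-172154 is given; its accumulation ratios correctly use C1D8. The effect is negligible. With a half-life of 1 h (Protocol 1.4.7 reports less than 1 h) and a 7-day interval, AUCtau/AUC0-inf = 1 − 2^(−168/1) = 1.0000.

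**The case against.** The strongest reply is that the baseline problem is derivative: the SAP plans no PD analysis, so its default rule is never applied to PD data. That is right about order, and it is why the omission leads. But SAP Section 2 still lists the cytokine outcome, and restoring the analysis without a baseline rule would leave it not computable.

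A second reply is that SAP Section 1 covers data drawn mainly from case report forms, so PD may be reported elsewhere. That is possible. But PK and ADA, also central-laboratory data, are in the SAP; no separate PD plan is cited; and Protocol 9.2 would still call for the move to be recorded in the SAP.

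A third reply is that the cytokine outcome is only exploratory. That stands and limits the weight of the point.

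A reader might also infer more than the documents support:

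- **That all 63 subjects lack a baseline.** The figure is a planning maximum under the current schedule. The SAP covers every protocol version. The version 1.0 change log (Protocol 16.7) records the removal of predose and 2-hour cytokine samples from the MIRV schedule, so some subjects enrolled under v0.0 may have an earlier sample. Their number is not given. The log also shows that receptor occupancy and expansion cytokines were added only in v1.0.
- **That the PD population is empty for PLD.** Protocol 9.2.1 does not define baseline, so this holds only if the SAP default is imported, and on the current schedule. The same log records removal of PLD biopsies.
- **That dose selection is undermined.** The safety monitoring committee reviews all available PD data as the trial proceeds (Protocol 14.1), so it does not depend on an SAP table.
- **That the omission was concealed.** The text shows only that it is not disclosed.

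**Conclusion.** The point holds and should be corrected before database lock. The SAP omits a protocol-specified population and analysis, and the Section 11 statement is therefore incorrect as written. That part follows directly from the text and needs no assumption; a separate PD plan, if one exists, would still have to be declared.

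Under the SAP's own baseline rule, the cytokine change-from-baseline outcome cannot be computed for up to about 63 planned subjects. This rests on planned enrolment, the current sampling schedule, and the absence of any PD-specific baseline elsewhere in the SAP. For receptor occupancy the consequence is indirect and conditional.

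The harm is to the completeness and transparency of the final PD report. Nothing here touches the dose-escalation rules, the safety analyses or the response analyses.

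**What to change.** 1. **SAP 5.3.2:** add that for blood cytokines and receptor occupancy, baseline is the last value before the first SL-172154 dose (scheduled at C1D8 predose), and that this value follows PLD or MIRV. Tumour biopsies keep the default. The same anchor then serves subjects from every protocol version who have that sample, including any with an earlier one.
2. **SAP Sections 4 and 13, plus a short PD section:** restore the PD population, using the baselines in item 1, and the descriptive summary by dose level and regimen. Alternatively, state in Section 11 that these are omitted, or where they will be reported.
3. **SAP Table 9:** change C1D1 to C1D8 in the CL and Vz rows, a one-word correction in each.

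The cost is a few sentences, one population row and PD table shells, or a single declaration in Section 11. No new samples are needed. The drawback is interpretive: changes from C1D8 predose describe SL-172154 added after PLD or MIRV, not change from an untreated state, and every such output must be labelled accordingly.
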